20.8. Monitoring of adverse events

Subjects with adverse events will be monitored by appropriate clinical assessments and laboratory tests as directed by the investigator. All adverse events should be tracked until their satisfactory resolution or their

stabilisation. All actions taken and monitoring results should be recorded in the appropriate section of the data collection notebook. If abnormalities in laboratory values are clinically significant and result in clinical symptoms or meet the criteria for a serious adverse event, the diagnosis shall be reported as a serious adverse event.

20.9. AAG notification, expedited notification and notification of pregnancy

Serious Adverse Event Notification

All serious adverse events (as defined below), whether or not they are considered treatment-related or expected, should be reported to the Pharmacovigilance department by the principal investigator or a collaborator within **24 hours** (one working day) of becoming aware of them, using the appropriate reporting form. Serious adverse events occurring at any time from the patient's randomisation into the study until the subject completes or leaves the study must be reported. A subject is considered complete: upon completion of the last visit or contact (e.g., telephone contact with the investigator or a collaborator) as indicated in the protocol evaluation schedule or after the last dose of study medication, whichever is later. Withdrawal is defined as the date on which a subject and/or the investigator determines that the subject can no longer meet the study requirements at any subsequent visits and assessments. AAG follow-ups will follow the same form indicating follow-up and should be submitted within 7 days, (noting that it is the "follow-up" form). The follow-up report will indicate whether the event has resolved or is still active, whether and how it has been treated, and whether the patient's participation in the trial has continued or ended. The trial site will retain the form.

The notifying investigator should complete and sign the AAG notification form (Annex 4) for the trial and send it by fax or e-mail to:

PhD [name]

Head of Pharmacovigilance

[contact]

E-mail: [contact]

The PV staff shall review the form received and, if appropriate, request additional information from the investigator. The investigator shall provide information to the sponsor or to the person assuming the tasks delegated by the sponsor (PV Manager) whenever requested to do so, and in any case when the investigator's initial assessment of severity or causality changes.

The reporting procedure described above shall be followed for communicating follow-up information.

The original copy of the AAG Forms (either initial or follow-up) shall be retained at the trial site, along with all other trial documentation.

The PV manager shall keep a detailed record of all AAGs or of special interest reported to him/her by the investigators.

In the event that a medication error occurs or the investigational medicinal product is used outside the protocol during the conduct of the trial, the investigator shall notify the VF manager within 24 hours of becoming aware of it. The reporting circuit and form will be the same as for AAGs.

Serious adverse events are those AEs that meet the severity criteria described in the definitions section. Clinically significant events that not life-threatening, life-threatening or require hospitalisation may be considered as serious adverse drug experiences when, based on sound medical judgement, they are likely to endanger the subject or require medical or surgical intervention to prevent one of the outcomes listed in this definition. Examples of such medical events are allergic bronchospasm requiring intensive, home or emergency department treatment, blood dyscrasias or seizures not resulting in hospitalisation, or development of dependence or substance abuse.

Laboratory test abnormalities that are considered clinically relevant also need to be reported, unless otherwise stated in this section of the protocol.

Expedited notification of RAGIs

The sponsor or the person delegated by the sponsor is responsible for notifying the EMA/AEMPS and the Autonomous Regions where the trial is conducted of all RAGI collected in the study, following the procedure indicated in the legislation in force.

The maximum period for notification of an individual case of suspected RAGI shall be 15 calendar days from the time the sponsor becomes aware of the suspected RAGI. Where the suspected RAGI has resulted in the death or endangerment of the patient, the sponsor shall submit the information within 7 calendar days of becoming aware of the suspected . He/she shall complete the information, if possible, within 8 days.

This information should include an assessment of the significance and implication of the findings, including relevant previous experience with the same or similar medicinal products.

Likewise, the competent body of each of the Autonomous Communities where the trial is carried out should be notified of suspicions of RAGI occurring in the centres.

health services in your Community. In both cases, the RAGI notification form shall be used for this purpose.

Expedited notification of other relevant safety information

The sponsor or its delegate should report as soon as possible and no later than 15 days after becoming aware of it any information that could change the risk/benefit balance of the investigational product (e.g. an increase in the rate of occurrence of expected AGRs, AGIRs occurring after completion of a clinical trial, new events related to the conduct of the trial or the development of the investigational product, any recommendations of the data monitoring committee relevant to subject safety, etc.).

Pregnancy Notification

In the event of any pregnancy occurring during the conduct of the trial, the investigator shall notify the sponsor or the person assuming the tasks delegated by the within 24 hours of knowledge of the pregnancy. The pregnancy will also be followed up to document the outcome of the pregnancy and the health status of the newborn. If the outcome of the pregnancy meets GABA criteria or if the newborn presents a serious event, the procedures described for GABA notification will be followed. Notification shall be made using the specific pregnancy notification form (Annex 5) which shall be sent by e-mail to the same contact person who will receive the HCA notifications.

The original copy of the Pregnancy Form will be kept at the trial site, along with the rest of the study documentation.

20.10. Blind opening and unmasking

Not applicable as the study is open-ended and therefore there is no blind.

20.11. Periodic security report

The annual safety reports, which will include the RAGIs and AAGs collected in the study from the time the patient is randomised, will be sent by the sponsor or the person delegated by the sponsor to the AEMPS (Clinical Trials Area of the Subdirectorato General for Medicines for Human Use), to the corresponding Autonomous Regions and to the CEIm, within the deadlines established in the legislation in force.

The submission of the annual safety report and other safety reports by the developer shall in any case comply with the criteria and procedure specified in Articles 43, 45 and 53 of Regulation (EU) No 536/2014 of the European Parliament and of the Council of 16 April 2014 and in accordance with RD1090/20015.

20.12. Report to researchers

The sponsor will submit safety information that could impact the safety of the patients enrolled in the trial to the investigators as early as possible. In addition, the investigator will be informed throughout the study of any safety issues, including protocol modifications due to safety concerns.

21. Statistics

For the calculation of the sample size we estimated an average annual number of laparoscopic cholecystectomies of 300 cases. Assuming a minimum recruitment rate of 50% in the study, a duration of 12 months and possible losses of patients, we estimate a sample size of 200 patients.

Since the main objective is to analyse whether there are differences between the doses and administration times of the 4 treatment groups in which categorical variables will be measured, the effect of the chosen sample size ($n=200$) on the statistical contrasts in this type of variables is $w=0.25$ with a power.95 and a significance error of the null hypothesis $\alpha=0.05$.

The procedure used to account for missing, unused and erroneous data will be the "*Pairwise Delection*" method. The confidence intervals of the statistics will be 95% and the contrasts will be performed at a significance level of 5%. All analyses will be performed with the free software R (version 4.1.2+, R Core Team, Vienna, <https://www.R-project.org/>) and the RStudio interface (version 1.4.1103+).

The study will have no planned intermediate analyses as no partial analysis of results is envisaged. Once all data have been collected, verified and validated, a statistical analysis of the data will be performed according to the specifications described in the protocol. If this analysis leads to the conclusion that further analysis is necessary, this will be reported in the final analysis of results. All treated and evaluable subjects shall be analysed. Different statistical tools will be used depending on the nature of the variables collected in the study, accompanying the results with their corresponding graphs.

Lilliefors-Kolmogorov-Smirnov and Shapiro-Wilks tests shall be performed to study the normality of the distribution of quantitative variables, and to their distribution they shall be represented by the mean (standard deviation) or the median (median deviation) and may be accompanied by their corresponding confidence intervals. The relationship between such variables shall be measured with Pearson's or Spearman's correlation coefficients.

The distributions of the categorical variables will be studied by means of frequencies and percentages. To represent and measure the dependence between them, contingency tables will be used with Pearson's Chi-square test, Fisher's exact test, McNemar's test

or Cochran's Q. A category comparison study could also be done using odds ratios between categories of clinical interest. To study the influence that some categorical variables might have on quantitative variables, ANOVA tests could be performed.

Finally, all the statistical information obtained on the relevance of each variable in the study could be used to apply classification tools to the individuals in the study (decision trees, logistic regression, ROC curves).

22. Direct Access to Source Data/Documents

The Promoter will enter into appropriate arrangements to appoint a monitor to oversee this study and to liaise regularly with the site, including arranging site visits. The investigator agrees to allow the monitor direct access to all relevant documents and to give his/her time and that of his/her staff to the monitor to discuss the results and any issues of concern.

23. Quality Control and Quality Assurance

In order to ensure the quality of the data, the promoter:

- Provide quality instruction and training to the research staff prior to the start of the study. Training topics include, but are not limited to: Good Clinical Practice (GCP) certificates, Adverse Event (AE) reporting, study details and procedures, study documentation, informed consent, and patient recruitment.

- Conduct regular monitoring in accordance with the International Conference on Harmonisation (ICH) for Good Clinical Practice (GCP). Data will be assessed for compliance with the protocol and for accuracy in relation to the source documents. Monitors will verify that the clinical trial is conducted, that data are generated, documented and reported in compliance with the protocol, good clinical practice and any applicable local regulatory requirements.

Direct access to the data should be granted to the PIs, monitors, members of the evaluating IRB/IEC and AEMPS, as well as to the authorities as necessary, to allow for study-related monitoring and surveillance, audits and inspections. At each site, they may review the trial records and compare them directly with the source documents, may discuss the conduct of the trial with the investigator, and may verify that the facilities are maintained in an acceptable manner. Audit reports will be treated confidentially.

24. Ethical and legal aspects.

The trial will be conducted in accordance with the recommendations for clinical trials and drug evaluation in man, as contained in the 1964 Declaration of Helsinki, as revised in Tokyo, Venice, Hong-Kong, South Africa, Edinburgh, Washington, Tokyo and Seoul, Fortaleza (2013) and in the AEPMS Instructions for the conduct of clinical trials in Spain (Version 9 of 27 July 2018). The investigator will conduct the study in compliance with the ethical principles of the Declaration of Helsinki.

The study/trial must adhere to the protocol, which ensures compliance with Good Clinical Practice, as described in the ICH Tripartite Harmonised Guidelines for Good Clinical Practice.

This study/trial will be submitted for evaluation by a Medicines Research Ethics Committee and notified to the AEMPS.

25. Data Management and Archiving of Records

The confidentiality of individual patient data will be respected at all times. The original data will be kept in the relevant department and will only be accessible to the study/trial investigators or to inspectors in case of inspection the Spanish Health Authorities.

Patients in the study/trial will be identified by a patient code. The investigator will inform patients that data collected during the study/trial will be stored and analysed electronically, in compliance with Regulation (EU) 2016/679 of the European Parliament and of the Council of 27 April 2016 on the protection of individuals with regard to the processing of personal data and on the free movement of such data and with Organic Law 3/2018 of 5 December on the Protection of Personal Data).

The researcher is the only person who can and should know the origin of the data obtained and who can associate it with the patient.

The personal data (full name, address, place of work, VAT number) of the investigators will be recorded in a computer file, for the sole purpose of facilitating the organisational and logistical aspects necessary for the conduct of the study/trial.

In compliance with the above regulations, the data file will be treated confidentially and researchers may exercise their rights of access, rectification, cancellation and opposition with respect to the personal data recorded, if they so request by writing to the Data Protection Officer of the promoter at [contact]

26. Financing and Insurance

The trial sponsor is responsible for ensuring that an insurance or financial guarantee is in place to cover damages incurred as a result of the clinical trial.

This clinical trial is considered a low-intervention level clinical trial accordance with RD 1090/2015 and European Regulation No. 536/2014 due to the following conditions:

1. The medicinal product (indocyanine green) studied in the present project is used in accordance with the authorised label.
2. In the present trial, no additional procedures are performed with respect to those that would have been performed on participants in the context of routine clinical practice, both in Spain and in the European Union and other international settings.

Therefore, and in accordance with chapter III, article 9 of Royal Decree 1090/2015: "Damage to the study subject that may result as a consequence of a low-intervention clinical trial will not need to be covered by an insurance contract or financial guarantee, if they are covered by the individual or collective professional liability insurance or equivalent financial guarantee of the healthcare centre where the clinical trial is carried out"; no *ad hoc* insurance has been taken out for this clinical trial.

27. Other test procedures. Management Delivery of other test materials

No "extra" materials are required for the realisation of this CE. All materials are available at participating CE centres.

Details of the documentation to be submitted to the Protocol are set out in Annex 2.

28. Audits and inspections

Health authorities or IRB/IECs may visit the site to conduct audits or inspections with verification of the original data. The objective of this audit is to systematically and independently evaluate all trial-related activities and documentation to determine whether these activities have been performed and whether the data have been analysed and reported in accordance with the protocol, GCP Standards, ICH Guidelines, and legal requirements.

29. Changes to the protocol

If an amendment to the trial protocol is necessary, the amendment or a new version of the trial protocol (amended protocol) should be notified to the IRB/IEC for approval by the IRB/IEC and, if applicable, also by the health authorities, prior to implementation. Local requirements should be met.

If an amendment to the protocol requires a change in the informed consent for a particular site, the IRB/IEC must be notified. Approval by the IRB/IEC is required prior to use of the new version of the consent form. The sponsor will distribute the amendments and new versions of the protocol to each principal investigator, who in turn is responsible for distributing these documents to the site staff. The distribution of these documents to the health authorities will follow the applicable regulations.

30. Difficulties and limitations of the study

Some of the difficulties could be found in the period of patient selection and inclusion in the study, due to the presence of numerous exclusion criteria. Other difficulties arise during the intervention, due to alleged problems arising from the use of fluorescent technology or laparoscopic surgical equipment. The subjectivity inherent in the visual assessment of the target variables and the presence of the surgeon factor is another limitation of the study. Finally, four groups with specific doses and administration periods are being evaluated, which could lead to the establishment of multiple different combinations, although methodologically impossible to carry out with an adequate number of cases.

31. Periodic Security Reports (DSUR)

Following the standards of good clinical practice and current regulations, the Pharmacovigilance Officer will prepare a safety report once a year. This report will contain the safety assessment of the drug according to all AAGs received by the Node's Pharmacovigilance Officer.

The Pharmacovigilance Officer will send the DSUR to the Project Manager for review, indicating the need for a response within 15 days and the deadline.

The Pharmacovigilance Officer will then send the DSUR to the Sponsor for approval, indicating the need for a response within 15 days and the deadline.

All modifications suggested by the GP or sponsor will be carried out by the Pharmacovigilance Officer.

The latest version of the DSUR will be signed by the PV manager, then by the GP (as reviewer) and finally by the developer giving his approval.

The annual safety report (DSUR) shall be sent by the developer to:

- AEMPS: via ECM portal using "E iv) Annual Safety Report (DSUR) [Only AEMPS]"
- CEIm del Área de Salud de Salamanca: via ECM portal using "E ii) Trial progress "
- Contact points for clinical trials in the Autonomous Communities via email (<https://www.aemps.gob.es/investigacionClinica/ptoContacto.do>)

The Project Manager will send a copy of the acknowledgement of receipt from the AEMPS to the Pharmacovigilance Officer.

Follow-up and completion reports

The Sponsor, in accordance with the current regulations and instructions regulating clinical trials by the AEMPS, will send the relevant follow-up reports.

Three months after the completion of patient enrolment, a statistical report including all results of the study shall be drawn up. This report shall be made available to the participating investigator. In addition, copies of the report shall be sent to the IRB that evaluated the study and to the AEMPS.

Any report obtained from this study will be treated as confidential, at least until it has been reviewed and analysed by the person responsible for the study. The data set may be used for general publications, which should always refer to the study. The investigator agrees not to provide information related to the study or to provide access to the study data to third parties.

32. Publication Policy

Regardless of the results of the study, the sponsor agrees to present them to the medical community through scientific publications, conferences or other means.

Any formal presentation or publication of the results of the study shall be considered a joint publication by the investigator(s) and the sponsor.

33. References

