 - Indication for surgery [Symptomatic cholelithiasis (biliary colic, acute cholecystitis, choledocholithiasis, acute ascending cholangitis, acute lithiasic pancreatitis), gallbladder polyps, gallbladder adenomyomatosis].
- **Perioperative period:**
 - Date of entry (dd-mm-yyyy).
 - Time of entry (hour:minutes)
 - Date of surgery (dd-mm-yyyy).
 - Time of surgery (hour:minutes).

- Type of surgery (elective/early/ delayed emergency).
 - Grade of cholecystitis in case of early surgery / delayed emergency (18th Tokyo Classification).
 - Intervention group (group 1/group 2/group 3/group 4).
 - Characteristics of the procedure. IV dosage (fixed dose/weight-adjusted dose). IV administration interval (>3 hours preoperatively, 15-30 minutes preoperatively). Immediate adverse reactions (yes/no. Specify). Number of trocars (3/4). Imaging system used (Olympus/Karl-Storz/Stryker). Optics used (0º/30º). Gall bladder puncture/emptying (yes/no). Bile culture (yes/no). Result of bile culture if any (specify).
 - Conversion to laparotomy (yes/no), intraoperative complications (yes/no), specification of intraoperative complications (cystic artery injury, right hepatic artery injury, liver injury with/without bleeding, gallbladder opening (intrapertitoneal biliary contamination: yes/no, lithiasis outflow into peritoneal cavity: yes/no), hollow viscus perforation, trocar bleeding, other). Operating time (minutes).
- **Postoperative period:**
 - Hospital stay (days), postoperative complications (intra-abdominal haematoma, bilioma, abscess, paralytic ileus, surgical site infection-ISQ, trocar evisceration, trocar eventration, others), postoperative complications according to Clavien-Dindo classification, bile duct injury (Strasberg classification), time of diagnosis bile duct injury (intraoperative / postoperative), treatment of bile duct injury (immediate surgical, radiological, endoscopic or delayed surgical). Mortality during admission (yes/no), 30-day mortality (yes/no), causes of mortality (specify). Adverse drug reactions within 30 days (yes/no. Specify).

All preoperative data will be collected for patients withdrawn from the study, as well the type of complication developed and any adverse events during the first 30 days of the study (if any). Subjects will not be replaced in the study. The follow-up period will be identical for subjects who do not undergo the study intervention.

15. Monitoring

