- **Group 4.** Weight-adjusted dose (0.05 mg/kg total body weight) with immediate pre-operative administration of the IV (15-30 minutes prior to surgery).

Verdye contains the active substance VI sodium powder for solution for injection. Each ampoule contains 25 mg of active substance. The dissolution medium for the product should be water for injectable preparations. The solution for injection should be inspected before administration and discarded in case of turbidity. The drug solution shall be prepared with 10 ml of water for injectable solutions, obtaining a ratio of 2,5 mg/ml. Once the solution is prepared according to the above protocol, it shall be injected directly through a peripheral venous line of the patient's upper limb. The medicinal product should be stored at a temperature below 30°C, keeping its original outer packaging in order to protect the medicinal product from light. Once the solution for injection has been prepared, it should be protected from light and used immediately.

The expected duration of subject participation will be 31 days, including preoperative, intraoperative, immediate postoperative (<24 hours), early postoperative (<7 days) and late postoperative (<30 days) periods. The patient recruitment period will be 12 months. The end of the clinical trial will take place from day 30 after discharge of the last patient recruited, with the aim of analysing the 30-day morbidity and mortality of the study patients.

* El periodo de lista de espera quirúrgica podría variar entre pacientes según necesidades asistenciales.

** El periodo postoperatorio normal tras colecistectomía laparoscópica programada es de 24-48 horas. No obstante, puede ampliarse debido a complicaciones y/o necesidades.

The frequency of patient visits will be as follows:

- 1- **Consultation prior to admission.** The objective of the study and the entire study protocol will be explained, along with the delivery of the HIP and the IC.
- 2- **Visit prior to surgery.** This visit will corroborate the correct understanding of the information, the presence of the correctly signed ICs and the resolution of any doubts or problems.

- 3- **In-hospital post-operative visits.** These will be carried out daily in the morning shift (8-15 hours). No different from postoperative visits of other operated patients.

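### The stated power of .95 for w = 0.25 at n = 200 fits only a 1-df contrast, not the planned four-group comparison, and the recruitment inputs given do not yield 200 without an unstated assumption

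*Protocol*

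**What the plan says.** Protocol section 21 (Statistics) builds the sample size from feasibility: "we estimated an average annual number of laparoscopic cholecystectomies of 300 cases". It continues "Assuming a minimum recruitment rate of 50% in the study", "a duration of 12 months and possible losses of patients", and arrives at "we estimate a sample size of 200 patients". No loss rate is given. The text does not say whether 300 is per centre or for all centres together.

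The next paragraph takes n = 200 as the chosen size and says that, for categorical variables compared across the four treatment groups, the corresponding effect is w = 0.25 "with a power.95 and a significance error of the null hypothesis" of 0.05. Degrees of freedom are not stated.

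Four other places bear on this:

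- Section 18 says "The patient recruitment period will be 12 months", and sets 1:1:1:1 allocation to four groups.
- Section 14 says of withdrawals "Subjects will not be replaced in the study".
- Section 21 restricts the analysis to treated and evaluable subjects, and names Pearson's chi-square on contingency tables among the tests.
- SAP section 2 calls for a comparison of G1, G2, G3 and G4 on each main variable. Twelve of these are yes/no, one has three levels (perceived usefulness) and three have five levels (degree of identification before and after dissection, and liver background).

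The SAP has no sample-size calculation, so section 21 holds the only power statement.

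**The concern.** There are two separate problems in section 21.

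The first is the power figure. The power of a chi-square test for a given w depends on n and on the degrees of freedom. A four-group table cannot have fewer than 3 df, yet w = 0.25 with power .95 at n = 200 looks like a 1-df result.

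The second is the derivation of 200. The three quantified inputs multiply to 150, and losses can only reduce the number evaluable.

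What is at stake is how the result is read. A reader who accepts .95 would take a null four-group comparison as strong evidence against an effect of w = 0.25, because the risk of missing it is stated as 5%. At 3 df and n = 200 that risk is about 14%, and at 12 df about 38%.

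**Working it through.** **Inputs.** From section 21: n = 200, w = 0.25, α = 0.05, stated power .95; 300 cases a year; 50% minimum recruitment; 12 months. From section 18 and SAP section 2: four groups, with variables of two, three or five levels.

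**Formula.** df = (groups − 1) × (levels − 1). The noncentrality is λ = n·w². Power is the probability that a noncentral chi-square with that df and λ exceeds the central 95% point.

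**Step 1: reproduce the plan's figure.** λ = 200 × 0.25² = 12.5. With 1 df (critical value 3.841), power is 0.942, close to .95. No larger df comes close:

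| Comparison at n = 200 | df | Critical value | Power | n for .95 power |
|---|---|---|---|---|
| 1-df contrast (2 × 2) | 1 | 3.841 | 0.942 | 208 |
| 4 groups × yes/no | 3 | 7.815 | 0.856 | 275 |
| 4 groups × 3 levels | 6 | 12.592 | 0.758 | 334 |
| 4 groups × 5 levels | 12 | 21.026 | 0.623 | 414 |

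The last column is the λ needed for .95 power divided by w² = 0.0625. For 3 df this is 17.17 / 0.0625 = 274.7, so 275.

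**Step 2: losses from 200.** The protocol gives no rate, so these are assumptions. At 5% losses (190 evaluable), 3-df power is 0.836. At 10% (180 evaluable), it is 0.814.

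**Step 3: the recruitment sum.** 300 × 0.50 × 1 year = 150 before losses. Ways to reach 200:

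- a recruitment fraction of 200 / 300 = 66.7%;
- a duration of 200 / (150 / 12) = 16 months at 50%;
- 300 per centre at two centres, giving 2 × 300 × 0.50 = 300 recruits, less 33% losses (1 − 200 / 300).

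None of these is stated. The sum 150 / (1 − 0.25) = 200 also works numerically. But no 25% loss rate appears, and inflating for losses applies to a required number, not to a recruitment yield. If it was intended, the evaluable number would be 150 and the power statement should use that.

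**Step 4: power if only the floor were reached.** At n = 150, λ = 9.375. Power is 0.865 (1 df), 0.731 (3 df), 0.610 (6 df) and 0.473 (12 df). With an assumed 10% loss (135 evaluable), 3-df power is 0.680. With 20% (120 evaluable), it is 0.623.

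**Step 5: detectable effect.** For .95 power at 3 df, w = √(17.17 / n), which is 0.29 at n = 200 and 0.34 at n = 150.

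**The case against.** **The recruitment inputs do not fix a number.** The 50% is called a minimum, so 150 is a lower bound before losses, and 67% recruitment is consistent with it. The trial is multicentre, and section 14 refers to hospitals in Salamanca and Badalona. If 300 is per centre, two centres give 300 recruits, and losses would act in the right direction to bring that down to 200. This stands: the derivation is under-specified, and 200 is not excluded.

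**The power statement is conditional on n = 200.** Showing that 150 falls short of .95 does not refute it. This also stands, which is why the main point rests on the df at n = 200 and not on the recruitment sum.

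**A 1-df contrast could have been intended.** The design crosses two doses with two times, and a yes/no variable compared between doses, or between times, over all 200 patients would have 1 df and power 0.942. But section 21 refers to the four treatment groups and SAP section 2 compares G1 to G4. Neither document specifies a pooled two-way contrast as the main analysis.

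**Stronger readings that a reader might infer.** One is that the trial will stop at 150. Nothing closes enrolment there: section 21 sets 200 as the chosen size, and the no-replacement rule concerns withdrawn patients. Another is that 200 cannot be reconciled with the inputs on any reading. Step 3 lists readings under which it can, each resting on an unstated assumption.

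**Conclusion.** The power statement is wrong as written. For w = 0.25, α = 0.05 and n = 200, power is about .95 only at 1 df. For the four-group comparison in the plan it is 0.856, 0.758 or 0.623, according to the number of outcome levels, before any loss. This rests on the Pearson chi-square test that the protocol names, with all four groups in the table and the 5% level applied to each variable without adjustment.

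The derivation of 200 does not reproduce from its stated inputs. They give a floor of 150 before losses, and the gap is filled only by an assumption that is not written down. The n = 150 figures are conditional on that floor and do not predict the trial's final size.

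**What to change.** In protocol section 21:

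1. Name the primary variable and table, give its df, and restate power at the expected evaluable number. Alternatively, keep .95 power and state the detectable w: at 3 df, 0.29 for n = 200 and 0.34 for n = 150. If a pooled 1-df contrast of doses or of times was intended, say so there and in SAP section 2.
2. Correct the derivation: state whether 300 is per centre or in total, the expected (not only minimum) recruitment fraction, and the assumed loss rate, so that a reader can follow the path to 200 enrolled and to the number evaluable.

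Restating power needs no extra patients and no design change. Its cost is a less favourable stated power or a larger detectable effect. If the clarified inputs show that 200 is not expected within 12 months, the sponsor will have to choose between longer recruitment, more centres and a smaller stated n. The first two are more than rewording.
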